5.2 Exclusion Criteria

1. Current substance abuse / dependence for substances other than nicotine and THC, (i.e. alcohol, amphetamines, barbiturates, etc.)
 - a. A positive urine toxicology screen (excluding THC, tricyclic antidepressants, or benzodiazepines (if prescribed)).
 - b. Moderate or severe cannabis use disorder.
2. Diagnosis of major mood disorder or other Axis I disorder other than schizophrenia or schizoaffective disorder as determined by a SCID
3. Current or recent suicidal ideation – suicidal ideation with intent or plan (indicated by affirmative answers to items 4 or 5 of the Suicidal Ideation section of the baseline C-SSRS) in the 6 months prior to screening or have a history of suicide attempt in the past 6 months or subjects who represent a significant risk of suicide in the opinion of the investigator.
4. Subjects who represent a significant risk of violence determined by the assessing clinician or PI, based on history, presentation, and the Buss-Perry Aggression Questionnaire ⁴⁸ or a rating of ≥ 5 on the BPRS hostility item.
5. Pregnant or nursing or positive urine pregnancy test.
6. Significant medical or neurological illness by history or physical exam, including seizure disorder, history of loss of consciousness lasting more than 30 minutes related to head trauma or intellectual developmental disorder.
7. Metal implants, such as a cardiac pacemaker, intra-cardiac lines, neurostimulator, medication infusion device, jewelry/piercings that cannot be removed, and/or any other metal in the body that cannot be removed.
8. Claustrophobia
9. A history of brain surgery
10. History of syncopal episode within the past 6 months
11. Cochlear implants
12. Skin disease at intended stimulation sites
13. The consumption of more than four alcoholic units within 24 hours before Intervention Visit 1 and 2, and any recreational drugs within 48 hours before Intervention 1 and 2

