2.4 Potential Risks & Benefits

2.4.1 Known Potential Risks

Risks of PLIFUS:

Because ultrasound has been used extensively for many years as a diagnostic tool in other fields of medicine, FDA safety regulations are well-established and well-validated. Some investigations of brain sonication have exceeded these safety guidelines and have not produced serious adverse effects. Theoretical adverse effects at very high levels of energy, far in excess of what will be used in this trial, include injury to brain tissue (lesions, bleeding, disruption of the blood-brain barrier) due to excessive heating or cavitation. In 704 human subjects who have been studied in 35 trials of transcranial ultrasound, no serious adverse events have been reported. Mild and transient side effects have been reported in 3.3% of subjects, including headache, neck stiffness, worsening mood, scalp heating, muscle twitches, cognitive effects (impaired attention), itchiness, sleepiness and anxiety⁴³. Rates of side effects associated with sham sonication have not been reported. The sonication parameters that will be employed adhere to FDA and ETC regulation standards for diagnostic and therapeutic ultrasound²⁸.

While PLIFUS is associated with only mild and transient side effects in healthy participants, it has not previously been studied in schizophrenia. It is possible that sonication of the Gpi might worsen symptoms of schizophrenia. If this happens, we expect it to be a transient effect, consistent with other behavioral effects. To minimize this risk, we will exclude from study individuals with a history of violence, aggression or suicidal behavior. We will be monitoring the severity of psychotic symptoms during sonication and will stop the procedure if symptoms worsen by more than 50% on AHRS and DESA or if the participant expresses clinically significant psychological distress or suicidal ideation. The study psychiatrist will remain with the participant during sonication and for 1 hour after completion of sonication to assess for worsening of psychosis and suicidality. The study psychiatrist will arrange for appropriate monitoring and further assessment after 1 hour if needed based on clinical judgement.

Risks of MRI:

A total of 7 MRIs will be performed using a Siemens 3T Prisma; one prior to the intervention visits and one preceding

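### The protocol contradicts itself on past suicidal behaviour and violence: section 5.2 admits some patients whom the summary, the risk section and the opening of section 5 bar

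*Combined protocol and SAP*

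**What the plan says.** **Broad statements.** Section 2.4.1, having said that sonicating the GPi could worsen schizophrenia symptoms, continues: "To minimize this risk, we will exclude from study individuals with a history of violence, aggression or suicidal behavior". Later in 2.4.1 the list of protective measures says that people with past suicidality are excluded. The Population entry of the Protocol Summary bars past violence and suicidal behaviour. The opening paragraph of section 5 does the same, specifies suicidal behaviour as attempts, and also requires that there be no suicidal ideation. None of these statements sets a time limit.

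**Numbered criteria.** Section 5.2 item 3 opens with "Current or recent suicidal ideation". It then limits this to ideation with intent or plan (C-SSRS ideation items 4 or 5) in the 6 months before screening, and adds those who "have a history of suicide attempt in the past 6 months" and "subjects who represent a significant risk of suicide in the opinion of the investigator". Item 4 covers "Subjects who represent a significant risk of violence determined by the assessing clinician or PI", a judgement "based on history, presentation, and the Buss-Perry Aggression Questionnaire", "or a rating of ≥ 5 on the BPRS hostility item".

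**How eligibility is decided.** Section 7.2.2 has it determined at screening from the inclusion and exclusion criteria. The same visit includes the psychiatric history, the C-SSRS and the BPAQ.

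**The concern.** The exclusion is more than a description of the population. Section 2.4.1 presents it as a step that reduces a named risk, in an illness in which the protocol says PLIFUS has not been studied. Section 2.1.1 adds that psychosis may contribute to violence. Someone who reads only the risk section would believe that no participant has ever attempted suicide or been violent. Someone who screens from 5.2 could enrol such a participant without departing from any numbered criterion. What is at stake is who is sonicated under a stated safety measure, and whether two members of staff working from different pages would reach the same decision.

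**Working it through.** No arithmetic applies, so the statements are set side by side.

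| Topic | Summary, 2.4.1, opening of section 5 | 5.2 items 3 and 4 |
|---|---|---|
| Suicide attempt | Any in the past; no time limit | Past 6 months only; otherwise at the investigator's discretion |
| Violence | Any in the past; no time limit (2.4.1 adds aggression) | Judged significant risk, or BPRS hostility of 5 or more |
| Ideation | None (opening of section 5; also 5.5) | Intent or plan in the 6 months before screening; otherwise at the investigator's discretion |

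**Test case 1.** A candidate attempted suicide two years before screening, reports no ideation with intent or plan in the last 6 months, and is not considered a significant suicide risk. No part of item 3 applies, so 5.2 admits the candidate. The summary, both statements in 2.4.1 and the opening of section 5 bar the candidate.

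**Test case 2.** A candidate once assaulted someone, is not judged a significant risk of violence, and has a BPRS hostility rating of 4. Item 4 does not apply: history feeds the judgement but does not exclude in itself, and 4 is below the threshold. Section 7.1.1 says that the BPAQ is given to assess past violence, but sets no score that excludes. So 5.2 admits the candidate, while the summary, the first statement in 2.4.1 and the opening of section 5 bar the candidate.

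**Could the broad wording be shorthand for 5.2?** A 6-month limit cannot be read out of an unqualified statement about the past. Section 5.2 itself separates the two forms: item 9 (brain surgery) has no time limit, and item 10 (syncope) states 6 months. The opening of section 5 goes as far as specifying attempts and still gives no window.

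**Ideation.** This is a lesser ambiguity. Item 3's lead-in sounds general, but its definition covers only intent or plan. The text therefore leaves open whether current ideation without either is acceptable, although the opening of section 5 rules it out.

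**The case against.** The strongest reply is that judgement closes the gap. Item 3 lets the investigator exclude for suicide risk, and item 4 requires history to be weighed. Clinicians are asked to refer only suitable patients (5.5). Bellevue inpatients must be thought safe and appropriate by their clinicians and continue only after discharge (5.5.2). Charts of Manhattan Psychiatric Center referrals are checked for violence (5.5.3). Protection also continues during treatment: staff "will stop the procedure if symptoms worsen by more than 50% on AHRS and DESA", or for marked distress or suicidal ideation. A psychiatrist stays for an hour after each session, and section 8 provides follow-up of suicidality at 24-48 hours and 7 days. All of this stands, and it limits the consequence. It does not remove the contradiction, because a judgement about present risk is not the categorical exclusion on history that 2.4.1 describes.

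Three stronger readings are tempting, and the documents support none of them.

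- **That the safeguard is simply not delivered.** The opening of section 5 is itself eligibility text, and 7.2.2 does not cite 5.2 by number. Staff face two conflicting rules, and it is not established that 5.2 prevails.
- **That a lifetime ban is what was meant.** Items 3 and 4 are specific enough, with C-SSRS items, a 6-month window and a hostility threshold, that 5.2 may equally be the intended rule and the other statements loose.
- **That an older attempt discovered after enrolment could not lead to termination.** Section 5.8.1 covers criteria recognised late, which include item 3's investigator-opinion clause, and has a separate best-interest ground.

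**Conclusion.** The contradiction is real and lies in current text. On suicide attempts, the rule is unlimited in the summary, 2.4.1 and the opening of section 5, and 6 months in item 3. On violence, it is a categorical exclusion in those places and a risk judgement or hostility threshold in item 4. Section 5.2 as written does not guarantee the safeguard stated in 2.4.1.

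The number of participants affected cannot be derived. The documents do not give the share of candidates with an older attempt or past violence. Nor do they fix the number sonicated: enrolment continues until 12 completers have good-quality imaging, with 4 more possible, so exposure can exceed 12 or 16. A probability of enrolling at least one such patient would only restate whatever share was assumed.

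The endpoints, the mixed model and the sample size are not affected. The point should be corrected because it concerns a participant-safety criterion and the correction is one of wording. The conclusion rests only on reading the sections as they stand.

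**What to change.** Adopt one rule and use it in every place. The sponsor should choose the direction, since the documents do not show which was intended.

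**Option (a): bring 5.2 up to the stated safeguard.**
- In item 3, exclude any lifetime suicide attempt. Keep the 6-month ideation criterion and the investigator's judgement.
- In item 4, make a history of violence toward others an exclusion in itself, defined (for example, a documented physical assault). Keep the judged-risk and hostility triggers.
- Bring the terms aggression and suicidality in 2.4.1 into line with items 3 and 4.
- Cost: a smaller eligible pool, of unknown size. The psychiatric history, C-SSRS and BPAQ are already taken at screening. The violence criterion should name its source, because a chart check for violence is described only for Manhattan Psychiatric Center referrals and records are reviewed only where available (7.2.1).

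**Option (b): if 5.2 is intended.**
- Reword the Protocol Summary, both statements in 2.4.1 and the opening of section 5 to match items 3 and 4.
- Let 2.4.1 rely on those limits together with clinician screening, monitoring and the stopping measures.
- Cost: a less favourable risk statement.

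**In either case,** state in item 3 whether current ideation without intent or plan excludes, and align the opening of section 5 and section 5.5 with the answer. Both options need an IRB-approved amendment (12.2). The consent form, which is not among the documents, would need a matching change only if it repeats the statement being altered.

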5.3 Inclusion of Subjects Using Marijuana

The incidence of cannabis use psychosis patients in the US is estimated at 40% to 60% and a serious concern has been raised that excluding individuals who use cannabis may bias samples and make results less generalizable to clinical populations. There is no reason to expect a negative interaction between cannabis and PLIFUS. We will record past use of cannabis and urine toxicology screen results for cannabis at screening. Self-report of cannabis use will also be recorded at the beginning of each intervention visit. We will include this as a factor in our analysis to assess whether cannabis use influences response to PLIFUS. The determination of moderate or more severe cannabis use disorder will be based on the Diagnostic and Statistical Manual (DSM) 5 criteria.

5.4 Vulnerable Subjects

We will not study children because schizophrenia is an illness of adulthood and because PLIFUS safety has not been sufficiently studied in children. We will not enroll individuals with decisional incapacity. We will assess potential participants for their ability to understand the procedure, the risks and alternatives and will document this with a true-false test about key issues regarding participation for which we will require 100% correct answers.

5.4.1 Assessment of Capacity

Assessment of capacity will be done by licensed MDs or nurses with experience treating this patient population. The assessors are study team members that are identified in Research Navigator. They do not need to be independent of the study because they are thoroughly trained to make this assessment and will verify the assessment of capacity by use of a true-false quiz that includes questions to determine that the potential participant understands the procedures, the risks and alternatives to participation and that participation is voluntary .

The individual performing the assessment and/or monitoring ongoing capacity will complete our standardized Assessment of Capacity Form and will administer a written 10 question true/false quiz to establish that the potential participant understands procedures, risks and alternatives to participation.

The results of the capacity assessment will be placed in the subject's study record.

Prospective subjects will be informed of the results of the capacity assessment after it's conducted. If an individual is found not to have the capacity to consent, the assessor will explain this to the individual. The individual will not be enrolled in the study. The assessor will provide the necessary resources and referrals for further care and evaluation.

5.5 Strategies for Recruitment and Retention

Participants will be help-seeking males or females, ages 18-55, meeting diagnostic criteria for schizophrenia or schizoaffective disorder and currently exhibiting at least moderate, continuous psychotic symptoms defined by a score of 4 or greater on at least one psychosis item of the BPRS (suspiciousness, hallucinations, unusual thought content, grandiosity) and in the absence of psychotomimetic substance use or other potential organic etiologies, or major mood disorder, and in the absence of suicidal ideation, pregnancy, or significant medical illness (including epilepsy).

Referring clinicians will receive the "Information for Clinicians" document, which contains information about the study as well as contact information for the study team.

Patients will be recruited at NYU Langone Health medical centers in Manhattan and Brooklyn, as well as Bellevue Hospital and Manhattan Psychiatric Center. Clinicians will be asked to only refer individuals who they believe are appropriate for the study and who are capable of deciding to participate. Once referrals are given, the study team will access EPIC to determine the participant's initial eligibility. [name] and the study coordinator will maintain relationships with clinicians at these institutions in order to generate referrals.

As detailed in [name] protocol for s22-01421, [name] and his staff may also ask current or former participants in this study if they are interested in participating in s22-01421. For any individuals who are interested, their preferred contact information will be shared with [name] team for them to reach out. Of note, only former subjects who indicated that they are okay with being contacted by [name] team in the future will be approached.

5.5.1 NYU Langone Hospital – Brooklyn and the Family Health Center

Subject recruitment will include collaboration with NYU Langone Hospital – Brooklyn and the Family Health Center at NYU Langone clinical leadership to help identify potential subjects. The clinical leadership team at FHC will utilize the inclusion/exclusion criteria developed by the study team to search the EPIC EMR and generate a list of potential subjects. This list will be screened to ensure that patients who have opted out of research recruiting are removed. The final list will be shared with the investigators who will then reach out to the patient's primary clinician, or another member of their clinical team, and see if they are willing to approach the patient and ask if they are interested in speaking to research staff about the research study. If the patient agrees, the member of the clinical team will connect the patient with the research team member.

5.5.2 Bellevue Hospital

Staff can refer patients from the Bellevue Adult Outpatient Psychiatry Clinic (OPC), Inpatient Psychiatry Units, and Comprehensive Psychiatry Emergency Program (CPEP) who are appropriate for study participation and willing to speak to an investigator, by reaching out to the study team with the MRN. The study team will then access EPIC to determine the patient's initial eligibility. If the patient seems eligible based on their chart, a psychiatrist/psychologist/nurse practitioner on the study team will assess the clinical appropriateness of the individual to participate in research and capacity to consent.

Consent and screening procedures can take place in the CPEP or Inpatient Psychiatry Units for those in which it is applicable. Of note, no screening laboratory procedures (urine drug screen, urine pregnancy screen) will take place for those who are screening in the CPEP and/or Inpatient Psychiatry Units. Following screening procedures, individuals who qualify, and who are judged by their clinicians to be safe and appropriate for participation, but still remain an admitted to the hospital, will continue in the study once discharged. Outpatients recruited from Bellevue can start screening at the OPC (including collection of urine laboratory specimens if the patient prefers to meet there instead of [name] or the [name] Imaging Center), or can begin/finish screening either at [name] or the [name] Imaging Center.

Of note, study staff may also come across potentially eligible patients at NYU Langone Manhattan, NYU Langone Brooklyn, and Bellevue Hospital via chart review or by participating in rounds. Study staff would first reach out to the patient's treating physician to inquire about appropriateness for participation and permission to contact the individual if deemed fit for screening.

The time required to complete recruitment and consenting will be variable depending on availability of clinicians. Potential participants will be allowed as much time as is needed to consider participation, including discussing this with family and their clinician. All interactions with potential participants will take place in private rooms to maintain confidentiality. Any identifiable data of screen failures will be destroyed immediately after the recruitment period has ended.

We will include individuals who speak Spanish as potential participants. In order to recruit Spanish speaking patients, our team will receive referrals from clinicians from our network of NYU-affiliated institutions and Bellevue Hospital. Clinicians who refer Spanish speaking patients will initially determine if the subject will be eligible to participate our study. If the patient qualifies and agrees to participate in our study, our team will provide a native Spanish speaking interpreter with training and understanding in medical terminology during the study visits. No Spanish-speaking participants will be enrolled until a modification is submitted to the IRB to provide the translated study documents.

5.5.3 Manhattan Psychiatric Center (OMH)

OMH MRNs will be shared by MPC clinicians with [name] via OMH internal emails. [name] will then review the charts of these patients for initial eligibility (check for MRI incompatibilities, violence, recent medication changes, etc.). [name] will obtain patient contact information either directly from the patient or via clinicians with the patient's verbal consent. Of note, the patient's consent for [name] to reach out will be documented in the OMH internal emails between her and the clinician. To clarify, the term "OMH" is used to describe the MRNs/charts/internal emailing system since OMH (Office of Mental Health) is the larger organization and MPC is the site we will be working with.

During the initial contact made with the patients, [name] will ask if it is okay to share a preferred method of contact with the NYU team, as well as provide the contact information for the NYU research team either verbally or through safe email (encrypted) with her NYU Langone email.

Of note, patients may also be introduced to the study team at their MPC clinic appointments, if the patient indicates this is okay with their clinician.

Since MPC clinicians are entirely in-person, one staff member at MPC may be used as a point person to speak to other clinicians about potential subjects (authorship can be offered to this individual).

5.5.4 Use of DataCore/Epic Information for Recruitment Purposes

We will use DataCore/EPIC for the recruitment of subjects via NYULangone MyChart. The study team will send a standardized recruitment message to the MyChart accounts of patients with a diagnosis of schizophrenia or schizoaffective disorder who are between 18 and 55 years of age. The recruitment message appears within the MyChart "Research Studies" activity tab and includes information about the study (i.e., the principal investigator, study coordinators, study name, and brief description). The tool enables patients to indicate whether or not they are interested in participating in the identified study, and this response is sent to the study team's Epic inbox. If an individual indicates that they are interested in participating, the study team will first reach out to their clinical team to determine the appropriateness of the individual to participate in research. After describing the study and providing the Information for Clinicians, research staff will ask: "Is the patient interested in participation in the study?" and "Is it clinically appropriate for this patient to participate in the study?". If the clinician reports that the patient is both interested and appropriate to participate, the study team will request the patient's preferred method of contact.

If the patient does not have an NYU and/or Bellevue affiliated clinician that they see regularly, the study team will contact them directly via MyChart.

Once contact is made, study staff will communicate to subjects the reason they are being contacted and will ask if they are interested in participating in this specific study. Should the potential subjects agree, the study team will provide the subjects with information regarding the next steps for participation.

We will also use DataCore/EPIC to generate and request two lists of patient names. Both requests will include patients that fit the following criteria for this study: diagnosis of schizophrenia or schizoaffective disorder, between 18 and 55 years of age, not deceased, not pregnant, and no request to opt out of research. One list will include patients who have visited the NYU Langone Hospital emergency departments (Manhattan and Brooklyn) and saw psychiatry hospital service in the past 6 months. The other list will include patients who have been admitted to the NYU Langone Inpatient Psychiatry Units (Tisch HCC10 and Brooklyn 5900) in the past 6 months. Study staff will request the standard SlicerDicer dataset with PHI including names and MRNs, as well as phone numbers and emails. Study staff will reach out to potentially eligible patients through this contact information. Subjects will be sent an IRB-approved REDCap screening survey or will be contacted on the phone using the IRB-approved phone recruitment script. All outreach efforts will abide to HIPPA policy. Of note, clinicians will not be contacted prior to reaching out to these patients as it is unlikely for them to have regular NYU and/or Bellevue clinicians since they are being identified from the ED and inpatient psych. If there is a clinician the patient sees regularly, this clinician will be reached out to, but if not, the patient will be contacted by the study team directly.

If a subject requests information regarding opting out of further recruitment for all research, subjects will be directed to contact [contact] or [name].

